3.6.2 Off-Study Criteria

- Patient is off-treatment including an approximately 30 day follow up visit (when logistically feasible)
- Patient's request to be withdrawn from the study

- Death

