- 2.1.2.11 Unable to avoid close contact or household contact with the following high-risk individuals for three weeks after the Day 1 vaccination: (a) children \leq 3 years of age, (b) pregnant or nursing women, (c) individuals with prior or concurrent extensive eczema or other eczemoid skin disorders, or (d) immunocompromised individuals, such as those with HIV.
- 2.1.2.12 Any condition which, in the opinion of the investigator, would prevent full participation in this trial (including the long-term follow-up), or would interfere with the evaluation of the trial endpoints.
- 2.1.2.13 Patients with prior chemotherapy for nonmetastatic prostate cancer within a year are excluded.
- 2.1.2.14 Receipt of an investigational agent within 28 days (or 56 days for an antibody-based therapy) before the first planned dose of study drugs. (Immune checkpoint inhibitors that are antibody-based will only require 28 days before enrollment)
- 2.1.2.15 Uncontrolled intercurrent illness including, but not limited to, ongoing or active infection, symptomatic congestive heart failure, unstable angina pectoris, cardiac arrhythmia, uncontrolled hypertension (SBP $>$ 170/ DBP $>$ 105) or psychiatric illness/social situations within 12 months that would limit compliance with study requirements.
- 2.1.2.16 Use of herbal products that may decrease PSA levels (e.g. saw palmetto)
- 2.1.2.17 Any gastrointestinal disease that could hinder the absorption of enzalutamide.
- 2.1.2.18 Patients who have had chemotherapy for metastatic castration-resistant prostate cancer. (Patients who have had docetaxel for metastatic castration sensitive disease per CHAARTED Data[34] may enroll as long as they did not have progressive disease

Short Title: Enzalutamide Vaccine in mCRPC

Version Date: 03/29/2022

while on docetaxel and are 6 months removed from treatment, with all treatment related toxicities resolving to at least grade 1.)

2.1.2.19 Patients who have received radiation therapy, radionuclide therapy or undergone surgery within certain duration (4 weeks) of enrollment

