3.6 CRITERIA FOR REMOVAL FROM PROTOCOL THERAPY AND OFF STUDY CRITERIA

3.6.1 Criteria for removal from protocol therapy

- Disease progression as evidenced by radiographic or clinical progression (defined in section [5.3.5](#)).
- Intercurrent illness or medical circumstances: if at any time the constraints of this protocol are detrimental to the patient's health, the patient may be removed from protocol therapy. In this event, the reasons for withdrawal will be documented.
- Patient's request to be taken off study. In this event, the reasons for withdrawal will be documented.
- If patients are non-compliant with the protocol guidelines, they may be removed from the study at the discretion of the principal investigator.
- Any Grade 4 toxicity that is possibly, probably or definitely related to the protocol treatment will require a patient to be off-treatment.
- Grade ≥ 3 autoimmune toxicity while on vaccine, will require a patient to be off-treatment.
- Any Grade 3 non-autoimmune toxicity that does not resolve to Grade 1 or baseline within 60 days and is possibly, probably or definitely related to the protocol treatment will require a patient to be off-treatment.
- Any grade of seizure will require discontinuation of enzalutamide but patients may continue vaccine at the discretion of the investigator.

Prior to documenting removal from protocol therapy, effort must be made to have all subjects complete a safety visit approximately 30 days following the last dose of study therapy.

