3.7 POST-STUDY EVALUATION

Patients treated at the NCI will be offered enrollment in the 04-C-0274 “Follow-Up Study of Subjects Previously Enrolled in Immunotherapy Studies Utilizing Gene Transfer” once off study.

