5 DATA COLLECTION AND EVALUATION

5.1 DATA COLLECTION

The PI will be responsible for overseeing entry of data into a 21 CFR Part 11-compliant data capture system provided by the NCI CCR and ensuring data accuracy, consistency and timeliness. The principal investigator, associate investigators/research nurses and/or a contracted data manager will assist with the data management efforts. Primary and final analyzed data will have identifiers so that research data can be attributed to an individual human subject participant.

All adverse events, including clinically significant abnormal findings on laboratory evaluations, regardless of severity, will be followed until return to baseline or stabilization of event.

Document AEs from the first study intervention, Study Day 1, through 30 days after last dose of study treatment. Beyond 30 days, only adverse events that are serious and related to study intervention need to be recorded.

An abnormal laboratory value will be considered an AE if the laboratory abnormality is characterized by any of the following:

- Results in discontinuation from the study
- Is associated with clinical signs or symptoms
- Requires treatment or any other therapeutic intervention
- Is associated with death or another serious adverse event, including hospitalization.
- Is judged by the Investigator to be of significant clinical impact

Short Title: Enzalutamide Vaccine in mCRPC

Version Date: 03/29/2022

If any abnormal laboratory result is considered clinically significant, the investigator will provide details about the action taken with respect to the test drug and about the patient's outcome.

End of study procedures: Data will be stored according to HHS, FDA regulations, and NIH Intramural Records Retention Schedule as applicable.

Loss or destruction of data: Should we become aware that a major breach in our plan to protect subject confidentiality and trial data has occurred, this will be reported expeditiously per requirements in section **6.2.1**.

As the toxicity profile of Enzalutamide, PROSTVAC-V TRICOM and PROSTVAC-F TRICOM is well defined and published, grade 1 clinical adverse events will not be recorded in the database.

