7.4 WAIVER OF EXPEDITED REPORTING TO CCR

As death due to disease progression is part of the study objectives, and captured as an endpoint in this study, it will not be reported in expedited manner to the sponsor. However, if there is evidence suggesting a causal relationship between the study drug and the event, report the event in an expedited manner according to section [7.3](#).

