Survival will be compared between the two arms, as a secondary endpoint, using Kaplan-Meier curves and a stratified log-rank test. Continuous parameters will be compared between the two arms using appropriate non-parametric tests, such as a Wilcoxon rank sum test. Immune outcomes and clinical outcomes will be compared using appropriate measures, such as Spearman correlation, Fisher's exact test, or Wilcoxon rank sum test. All secondary outcomes will be reported without formal adjustment for multiple comparisons but in the context of the number of such tests performed.

In order to allow for a small number of inevaluable patients, up to 76 total patients may be enrolled in order to yield 72 total evaluable patients. If the study is able to accrue approximately 2 patients per month, then accrual can be completed in approximately 3 years.

This projected accrual time frame is based on a previous trial in mCRPC which recently enrolled at the NCI. Trial 11-C-0195 enrolled 52 patients in under 2 years, therefore it would be feasible to accrue the number of patients required in this design.

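### Patients leave the study about 30 days after treatment ends and no later survival follow-up is specified, so the planned overall-survival comparison would be censored soon after progression

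*Combined protocol and SAP*

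**What the plan says.** Section 1.1.2 makes overall survival a secondary objective, and section 9 gives the analysis: "Survival will be compared between the two arms, as a secondary endpoint, using Kaplan-Meier curves and a stratified log-rank test". It states no number of deaths and no power for that test.

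Two rules in section 3.6 determine how long a patient is observed. Under 3.6.1, protocol therapy ends for several reasons, the first being "Disease progression as evidenced by radiographic or clinical progression". Under 3.6.2, a patient is off study when "Patient is off-treatment including an approximately 30 day follow up visit (when logistically feasible"; the other triggers are withdrawal by the patient and death.

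After off-study, section 3.7 says: "Patients treated at the NCI will be offered enrollment in the 04-C-0274" protocol, titled "Follow-Up Study of Subjects Previously Enrolled in Immunotherapy Studies Utilizing Gene Transfer". Section 5.1 limits safety recording: "Beyond 30 days, only adverse events that are serious and related to study intervention need to be recorded".

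Three places imply that later deaths are wanted. Section 7.4 waives expedited reporting with the words "As death due to disease progression is part of the study objectives, and captured as an endpoint in this study". An exclusion criterion in 2.1.2 covers conditions that "would prevent full participation in this trial (including the long-term follow-up". Section 4.3.3 wants samples kept linked to dates of death. None of them says who checks vital status, how, or how often.

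**The concern.** Taken together, 3.6.1 and 3.6.2 close a typical patient's record about a month after progression. If progression predicts death, patients are censored just as their risk rises, and the independent-censoring assumption behind Kaplan-Meier and the log-rank test fails. Time on study also depends on time to progression, the quantity that the vaccine is meant to change, so the amount of survival follow-up can differ by arm.

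Survival matters to this protocol's argument. Sections 1.2.3 and 1.2.7 describe earlier vaccine trials in which survival improved while time to progression did not. Few observed deaths, with follow-up tied to progression, would make the survival comparison hard to read in either direction.

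**Working it through.** **The plan's own figure.** Section 9 gives 52 events, a hazard ratio of 1.80 and one-sided alpha of 0.10. Schoenfeld's formula gives power = Φ(½·√52·ln 1.80 − 1.2816) = Φ(2.119 − 1.282) = Φ(0.838) = 79.9%, which agrees with the stated 80%. This calculation concerns progression only. There is no stated survival figure to reproduce.

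**Inputs for the survival check**
- 36 patients per arm, uniform accrual over 36 months, data cut at month 48 (section 9).
- Median time to progression 10 and 18. Section 9 labels these cycles, but its preceding paragraph gives 10 months; read here as months. Hazards λp = ln 2/10 = 0.0693 and ln 2/18 = 0.0385 per month.
- Off study at progression plus 1 month (3.6.1 and 3.6.2).
- Assumption, not given for this trial: the same median survival in both arms, 35.5 months (enzalutamide arm of the chemotherapy-naive phase III trial, section 1.2.1) or 25.1 months (vaccine arm of the randomized phase II trial, section 1.2.3).

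**Case (a): death independent of progression.** With λd = ln 2/35.5 = 0.01953, full follow-up gives 36·[1 − (e^(−12λd) − e^(−48λd))/(36λd)] = 36·[1 − (0.7911 − 0.3917)/0.7029] = 15.5 deaths per arm, 31.1 in all. Deaths seen on study are 36·∫ λd·e^(−λd·t)·P(TTP > t − 1)·G(t) dt from 0 to 48, where G(t) = 1 up to month 12 and (48 − t)/36 after it.

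**Case (b): every death follows progression.** Survival is time to progression plus an exponential post-progression time, scaled in each arm to give the assumed median. A death is seen if it falls within 1 month of progression and before the cut.

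| Median survival | Case | Deaths with full follow-up | Seen before off-study | Missed |
|---|---|---|---|---|
| 35.5 months | (a) | 31.1 | 17.5 (56%) | 44% |
| 35.5 months | (b) | 29.2 | 2.4 (8%) | 92% |
| 25.1 months | (a) | 39.3 | 23.0 (58%) | 42% |
| 25.1 months | (b) | 40.4 | 5.3 (13%) | 87% |

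**By arm.** In case (a) at 35.5 months, arm A shows about 7.5 of 15.5 deaths (49%) and arm B about 10.0 of 15.6 (64%), although true survival is identical. The gap comes only from arm B's longer assumed time to progression.

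**Without the cut.** In case (a) the probability that death comes before off-study is 1 − e^(−λd)·λp/(λp + λd). At 35.5 months this is 1 − 0.981·0.780 = 23% in arm A and 1 − 0.981·0.664 = 35% in arm B; case (b) gives 3% and 6%. This is relevant because accrual closed in December 2016 (6.5.2) and the current protocol is dated March 2022.

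**Reading the two cases.** Under strict independence, censoring at progression loses deaths but does not bias the log-rank test. Bias enters as progression becomes predictive of death, which is also where the loss approaches case (b).

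**The case against.** The protocol never says that survival is censored at off-study; that follows from reading 3.6.2 with section 9. Sections 2.1.2, 4.3.3 and 7.4 show that the authors meant to record deaths, and staff may be doing so. The study calendar in 3.4 is incomplete in the available text, so the lack of a survival row there proves nothing. This lowers the chance that deaths have actually been lost. It does not supply the missing method, schedule or censoring rule.

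A reader might infer from the gene-transfer title that the later follow-up study serves the vaccine arm alone. The documents do not support that. Section 3.7 offers it to patients treated at the NCI and names no arm; the title refers to subjects enrolled in gene-transfer studies, which can describe both arms; and its eligibility rules are not in the documents. What stands is that entry is voluntary and that nothing says its data return to this trial's survival analysis.

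A reader might also infer that time to progression is censored differently by arm, because off-study ends protocol scans and grade 3 or higher autoimmune toxicity on vaccine is an extra exit in arm B. No frequency is given, so no size can be put on this. The note in 5.3.5.4 also asks for every effort to document objective progression after discontinuation in patients with symptomatic deterioration. That note and 3.6.2 pull in different directions and need reconciling; no bias in the primary endpoint has been shown.

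**Conclusion.** The gap is real: a survival comparison is planned, patients leave the study about 30 days after treatment ends, and no readable section collects deaths after that. Under the stated assumptions, 42-44% of deaths by month 48 are missed if death is independent of progression and 87-92% if deaths follow it. The second model is clinically the more plausible, but the documents do not settle which applies. To say flatly that most deaths are missed is therefore too strong: at the 48-month cut it fails in the independent case.

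This should be fixed before survival is analysed. It does not threaten the trial's main conclusion. Survival is a secondary endpoint without stated power, sections 1.2.7 and 1.3 argue for time to progression as the endpoint for combination therapy, and the primary design (52 events, about 80% power) does not depend on survival follow-up.

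**What to change.** 1. Amend 3.6.2 and 3.7 so that off-treatment patients in both arms stay in survival follow-up on one common schedule, by telephone, medical record or public death records, until death, withdrawal of consent to follow-up, or data cut-off.
2. Ascertain vital status now for patients of both arms who are already off study, using the same sources and the same cut-off date.
3. State in section 9 that survival is censored at the date last known alive. Align 2.1.2, 4.3.3 and 7.4 with the procedure.
4. Reconcile 3.6.2 with the note in 5.3.5.4: for patients who stop without progression, use available routine-care scan reports to document later progression.

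The cost is a protocol amendment, a short call or record check per patient, and possibly approval to re-contact former participants. No treatment, study visit or procedure changes.

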3.7 POST-STUDY EVALUATION

Patients treated at the NCI will be offered enrollment in the 04-C-0274 “Follow-Up Study of Subjects Previously Enrolled in Immunotherapy Studies Utilizing Gene Transfer” once off study.

3.8 CONCOMITANT TREATMENT

Patients will be on concomitant androgen suppression therapy with a GnRH agonist or GnRH antagonist (unless they have had a prior orchiectomy). Patients may also be on concomitant drugs to prevent bone loss, including bisphosphonates and denosumab.

Other supportive care with blood components, antibiotics, analgesics, general medical therapy, etc., will be delivered as required. Use caution when co-administering medication which may lower the seizure threshold.

Consistent with the PREVAIL trial which demonstrated improved survival in mCRPC and led to FDA approval in the chemotherapy-naïve subgroup, palliative radiation will be allowed for patients on this study.

They will be allowed to continue enzalutamide (with/without vaccine). There is no concern for overlapping toxicity.[\[36\]](#)

3.8.1 Excluded medications

While patients on protocol treatment, all medications required for the health of the patient are allowed with the following exceptions:

- Concurrent chemotherapy
- Concurrent immunotherapy
- Concurrent anti-cancer radionuclides
- Concurrent systemic corticosteroid use (daily or every other day for continued use > **14 days**)
- Concomitant use of secondary hormonal treatments

3.8.2 Treatment of vaccinia vaccination complication

3.8.2.1 Vaccinia Immune Globulin:

First-line treatment of some of the complications of vaccinia caused by dissemination of vaccinia virus (severe cases of inadvertent inoculation involving extensive lesions or if comorbid conditions exist, severe cases of generalized vaccinia in patients that are systemically ill and whose condition might be toxic or who have serious underlying immunosuppressive illnesses, eczema vaccinatum, and progressive vaccinia) is with VIG.

VIG is contraindicated, however, for the treatment of isolated vaccinia keratitis. VIG is a sterile solution of the immunoglobulin fraction of pooled plasma from individuals inoculated with vaccinia vaccine. VIG is an investigational agent available through the CDC’s Strategic National Pharmaceutical Stockpile under an IND protocol by contacting the CDC’s Smallpox Vaccine Adverse Events Clinician Information Line at [name]. Upon receipt of a call from a patient or upon direct observation of a patient or contact who manifests signs and symptoms of any of the above conditions, the investigator should place a call to the CDC as soon as possible:

1. To initiate review of the clinical case,
2. To seek consultation on the appropriateness of VIG therapy,
3. To determine the appropriate VIG dose and dosing method for administration, if VIG therapy is required, and
4. To determine how to access and have the appropriate doses of VIG delivered.

Early institution of VIG therapy is advised following recognition of clinical symptoms compatible with some vaccinia complications (eczema vaccinatum, severe generalized vaccinia, progressive vaccinia, and some cases of inadvertent inoculation). The effectiveness of VIG therapy appears to be time dependent. VIG has not proven to be of benefit in the treatment of post-vaccinial encephalitis, and is contraindicated for treatment of isolated vaccinia keratitis due to the increased risk of corneal scarring.

A new intravenous formulation of VIG is available through the CDC, which has a lower level of aggregated protein, allowing it to be used by either the IM or IV route. This formulation will most likely be preferred for administration and investigators will be instructed by the CDC regarding appropriate dosing and method of administration based on formulation and availability. There is no guarantee that VIG will successfully treat complications. At present, there are no other anti-viral therapies of proven benefit for the treatment of vaccinia-related complications.

3.8.3 Cidofovir (Vistide®, Gilead Sciences)

Cidofovir is an FDA-approved antiviral drug for the treatment of CMV retinitis among patients with AIDS. Cell-based in vitro studies and animal model studies have demonstrated antiviral activity of this agent against certain orthopoxviruses. Currently, efficacy in the treatment of vaccinia-related complications in humans is unknown. According to the CDC, “VIG is recommended as first line of therapy. Cidofovir may be considered as a secondary treatment, and will only be released by the CDC after all inventories of VIG have been exhausted, after a patient fails to improve with VIG treatment, or as a last effort for a patient who is otherwise near death.” [Medical Management of Smallpox (Vaccinia) Vaccine Adverse Reactions: Vaccinia Immune Globulin and Cidofovir. Last updated February 11, 2003. Available at: <http://www.bt.cdc.gov/agent/smallpox/vaccination/mgmt-adv-reactions.asp>].

4 BIOSPECIMEN COLLECTION

4.1 CORRELATIVE STUDIES FOR RESEARCH

4.1.1 Parameters of Immune Response

(Refer to [4.1.2](#) Immunologic Assays for detail):

- IFN-gamma ELISPOT assay for PSA-specific T lymphocytes
- CD4 T Cell Proliferation
- Antibodies to PSA and other tumor antigens
- Leukocyte CD3, CD4, CD8 subsets; CD4:CD8 ratio will be drawn at baseline and each cycle while the patient remains on trial.
- Immunologic profiles will be investigated to evaluate whether enhanced thymopoiesis might be present during vaccine administration; these immunologic profiles are to include enumeration of recent thymic emigrants by quantification of T-cell subsets by multiparameter flow cytometry.

- The results of the HIV antibody test need to be available before treatment to determine eligibility.
- HLA class I expression (HLA typing) with A2 subtyping (obtain any time prior to first vaccine).
- Immunologic studies will be repeated more frequently if clinically indicated. Any abnormalities potentially related to treatment will be followed until they have resolved or have been determined not to be treatment-related.

4.1.1.1 All patients who are HLA A02 or A03 (approximately 50% of the US population) will undergo leukapheresis every 12 weeks while on-study when available and with the consent of the patient. Patients may refuse.

- IFN-gamma ELISPOT assay
- T cell proliferation
- Antibody Response
- Flow cytometry analysis of thymic emigrants
- Natural Killer (NK) Cells
- Regulatory T Cells
- Additional Assays: Blood samples may be used for additional research studies, which may include phenotypic and functional analysis of immune-cell subsets and analyses for cytokines, chemokines, antibodies, tumor associated antigens, anti-glycan antibodies and/or other markers.

Details on these tests can be found in [4.1.2](#).

4.1.1.2 **Collection of blood samples for immune assays:** Blood samples may be obtained at baseline, 1 month, 3 months, 12 months, 18 months, then every 6 months at restaging while on study. All patients will have 6 (10ml) green top tubes and 2 (8ml) SST drawn prior to treatment at designated timepoints.

4.1.1.3 The samples will be processed at:

Clinical Services Program
 NCI Frederick Cancer Research and Development Center
 [name]
 [name]
 [contact]

On days samples are drawn, [name] at CSP should be notified (phone: [name]; fax [name]). She will arrange courier delivery of the specimens to the processing lab.

4.1.2 Immunological Assays

4.1.2.1 IFN-gamma ELISPOT

We plan to examine the immune response in selected patients (HLA-A2-positive).

HLA class I expression (HLA typing) with A2 subtyping will be done prior to enrollment. Results will not be required prior to enrollment.

Lymphocytes will be separated from heparinized blood using density gradient centrifugation. The lymphocytes will then be placed in human AB serum with 10% DMSO and stored in liquid nitrogen. When samples are available from pre- and post-treatment, the ELISPOT assay will be performed. The ELISPOT assay, measuring IFN-gamma production, is used to determine CTL precursor frequency to peptides from PSA, PSMA, MUC-1, PSCA, CEA, and PAP in both pre- and post-vaccination peripheral blood mononuclear cells, as previously described [37, 38]. Briefly, 96-well mL HA plates (Millipore Corporation, Bedford, MA) are coated with 100 μ l/well of capture MAb against human IFN-gamma at a concentration of 10 μ g/mL for 12h at RT. Plates are blocked for 30 min with RPMI 1640 plus 10% human Ab serum 2×10^5 PBMC are added to each well. PSA-3A pulsed C1R-A2 cells are added into each well as antigen-presenting cells (APC) at an effector:APC ratio of 1:1. Unpulsed C1R-A2 cells are used as a negative control. HLA-A2 binding flu matrix peptide 59-66 is used as a positive peptide control [39]. We also perform each sample with 6 replicates to control for variability. In addition, each sample is run with a flu peptide control (pre- and post-vaccine) as well as samples from a “normal” control HLA-A2-positive individual with previously determined levels of flu-specific T-cell precursors. Cells are incubated for 24 h and lysed with phosphate-buffered saline (PBS)-Tween (.05%). Biotinylated anti IFN-gamma antibody diluted to 2 μ g/mL in PBS-Tween containing 1% bovine serum albumin (BSA) is added and incubated overnight in 5% CO₂ at 37°C. Plates are washed 3 times and developed with avidin alkaline phosphatase (GIBCO/BRL, Grand Island, NY) for 45 min. After washing the plates 3 times, each well is examined for positive dots. This assay will be performed in the Genitourinary Malignancies Branch, NCI, NIH. The number of dots in each well will be counted by 2 separate investigators in a *blinded manner*, and the frequency of responding cells will be determined.

